12.5.1 Death Classification and Reporting

Sufficient information will be required in order to properly classify the subject's death. The Investigator shall classify each subject death per the following definitions:

Cardiac Death: A death directly related to the electrical or mechanical dysfunction of the heart.

- Sudden Cardiac Death (SCD): Natural death due to cardiac causes, indicated by abrupt loss of consciousness within one hour of the onset of acute symptoms; preexisting heart disease may have been known to be present, but the time and mode of death are unexpected. If the time of onset cannot be determined, SCD will alternatively be defined as any unexpected cardiac death occurring out of the hospital or in the emergency room as dead on arrival.
- Non-sudden Cardiac Death: All cardiac deaths that are not classified as sudden deaths, including all cardiac deaths of hospitalized subjects on inotropic support.

Non-cardiac Death: A death not classified as a cardiac death.

Unknown Death Classification: Unknown death classification is intended for use only when there is insufficient or inadequate information to classify the death.

A Medical Advisor will review deaths and provide a final assessment of the primary cause of death and classification of death.

Regulatory reporting of Subject Deaths will be completed according to local regulatory requirements.

12.6 Product Complaint Reporting

It is the responsibility of the investigator to report all product complaint(s) associated with a medical device distributed by Medtronic, regardless whether they are related to intended use, misuse or abuse of the product. Reporting must be done immediately and via the regular channels for market-released products. The reporting of product complaints by the clinical team must be done according to the local Standard Operating Procedures. Medtronic will notify the RAs (e.g. CA) as applicable for the following incidents immediately upon learning of them and is not limited to AEs and DDs only:

- Any malfunction or deterioration in the characteristics and/or performance of a device, as well as any inadequacy in the labeling or instructions for use which led or might have led to the death or serious deterioration in the state of health of a patient, user, or other person.
- Any technical or medical reason resulting in withdrawal of a device from the market by the manufacturer.
- Any serious deterioration in the state of health, including:
 - Life-threatening illness or injury
 - Permanent impairment of a body function or permanent damage to a body structure
 - A condition necessitating medical or surgical intervention to prevent permanent impairment of a body function or permanent damage to a body structure

13. Medical Advisor Review

At regular intervals, a medical advisor will conduct a medical review of all adverse events.

Medtronic Business Restricted

If the sponsor disagrees with the investigator's classification of the event, the sponsor assessment will be provided to the investigator. If the investigator agrees with the sponsor assessment, the CRF documenting the AE will be updated accordingly.

If the investigator does not agree with the sponsor assessment, both determinations will be provided within the final report; however, the medical advisor's assessment will be used for data analysis. The disagreement will also be included in reporting to ECs and regulatory authorities, if required.

14. Statistical Design and Methods

14.1 General Aspects of Analysis

Data analysis will be performed by Medtronic statisticians or designees.

The cohort will include all enrolled subjects who undergo the study procedures unless the subject does not complete the required testing, and there are no pre-specified subgroups for assessment. For endpoints involving only measurements collected at follow-up visits, only subjects who complete those visits will be included in the analysis of those endpoints.

A Statistical Analysis Plan (SAP) will be developed and kept under separate cover and will include a comprehensive description of the statistical methods and analyses to be included in study reports. It will also include descriptions on how missing, unused, and spurious data will be accounted. Any change to the data analysis methods described in the CIP will require an amendment only if it changes a principal feature of the CIP. Any other change to the data analysis methods described in the CIP, and the justification for making the change, will be described in the clinical study report.

14.2 Primary Objective(s) Primary Objective for Safety: MRI-related Events

To demonstrate the safety of SureScan system CIED in clinical 3.0T MRI environment within 1-month post-MRI scan.

Hypothesis

The MRI-related event-free rate within 1-month post-MRI is greater than 90%.

$$H_0: p \leq 0.90$$

$$H_A: p > 0.90$$

Where p is the percentage of subjects free of an MRI-related event within 1-month post-MRI.

Endpoint Definition

For subjects with IPG devices, the occurrence of any of the following within 30 days after a 3.0T MRI procedure will be considered an MRI-related event:

- Medical advisor-assessed MRI-related complication within 30 days post-MRI

Medtronic Business Restricted

China CIED 3.0T MRI Performance Study Clinical Investigation Plan

MDT23009

Version 2.0

Page 42 of 60

Medtronic

- Medical advisor-assessed right ventricular MRI-related loss of capture within 30 days post-MRI

For subjects with ICD or CRT-D devices, the occurrence of any of the following within 30 days after a 3.0T MRI procedure will be considered an MRI-related event:

- Medical advisor-assessed MRI-related complication within 30 days post-MRI
- Sustained tachyarrhythmia originating during SureScan programming, requiring immediate treatment (defined as ATP, device shock, or external shock), as assessed by a medical advisor.
- Medical advisor-assessed right ventricular MRI-related loss of capture within 30 days post-MRI

Performance Requirements

[figure not shown]
The null hypothesis will be rejected if the one-sided 97.5% lower confidence bound is greater than 90% or, equivalently, if the p-value is less than 0.025.

Rationale for Performance Criteria

All events that can be attributed to the MRI are expected to occur within one month. There is no evidence of lingering effects of MRI scans on devices. Therefore, assessing this objective one month post-MRI will capture all MRI-related events that result following the MRI procedure.

Previous 1.5T MRI clinical studies including EnRhythm MRI, Advisa MRI and 5076 MRI for IPG devices and Evera MRI for ICD devices have used an Objective Performance Criterion (OPC) of 90% for a similar safety objective, and all of them have met their safety objective with 0 MRI-related events observed (Table 10).

Medtronic Business Restricted

Analysis Methods

The objective will be evaluated using a one-proportion binomial exact test along with a one-sided 97.5% lower (Clopper-Pearson) confidence bound. The proportion of subjects free from MRI-related events will be calculated by dividing the number of subjects without an MRI-related event by the number of subjects at risk for an event. The denominator is all subjects implanted with a SureScan study device who underwent a 3.0T MRI scan and completed the one month post-MRI scan visit or later follow-up, or have had an MRI-related event prior to completing the one month post-MRI scan visit. The numerator will be the subjects included in the denominator who are free from MRI-related events. Subjects who are lost to follow-up or withdraw for other reasons prior to the one-month post-MRI scan follow-up will not be included in the analysis unless they have had an MRI-related event.

To assess the robustness of this analysis to missing data, a tipping point analysis will be performed based on all subjects enrolled.

Determination of Patients/Data for Analysis

All subjects implanted with a SureScan study device who have a 3.0T MRI scan after enrollment and have completed their one month post-MRI scan follow-up, or have had an MRI-related event without completion of their one-month post-MRI scan follow-up will be included in the analysis.

14.3 Secondary Objective(s) Atrial and Ventricular Pacing Capture Thresholds

To characterize changes in atrial and ventricular pacing capture thresholds (APCT and VPCT) from pre-MRI to 1-month post-MRI scan

Hypothesis

There is no hypothesis for this objective.

Endpoint Definition

PCTs to be evaluated include:

- APCT of atrial lead for subjects with an IPG device
- APCT of atrial lead and VPCT of right ventricular (RV) lead for subjects with an ICD device
- APCT of atrial lead and VPCTs of right ventricular (RV) and left ventricular (LV) leads for those with a CRT-D device.

Medtronic Business Restricted

China CIED 3.0T MRI Performance Study Clinical Investigation Plan

MDT23009

Version 2.0

Page 44 of 60

Medtronic

PCTs of each subject will be measured prior to the 3.0T MRI scan and at the one month post-MRI. Change in PCT is defined as PCT measured at one month post-MRI subtracts that measured prior to a 3.0T MRI scan. Proportion of subjects with an increase less than or equal to 0.5V in APCT or VPCTs from pre-MRI to one-month post-MRI will also be used to characterize the efficacy performance of SureScan with respect to PCTs.

If the 1-month post-MRI APCT or VPCT is missing, the PCT measured immediately post-MRI will be used instead.

Performance Requirements

There are no performance requirements.

Rationale for Performance Criteria

The 0.5V threshold for the increase in a PCT from pre-MRI to one-month post-MRI is consistent with what have used in the FDA approved pre-market MRI studies such as EnRhythm MRI, Advisa MRI, and Evera MRI.

Analysis Methods

The change in PCT is the PCT measured at one month post-MRI subtracts that measured prior to a 3.0T MRI scan. Descriptive statistics such as mean and standard deviation will be provided for changes in APCT and VPCTs, respectively.

In addition, the percentage of subjects with an increase less than or equal to 0.5V from pre- to one month post-MRI in APCT and VPCTs will be determined.

Determination of Patients/Data for Analysis

To be included in the analysis, all of the following must be met:

- The subject must undergo a 3.0T MRI scan.
- The subject must have valid PCT measurements pre and post-MRI (see paragraph below for definitions).
- The (atrial, right or left ventricular) lead is not dislodged within 6 weeks prior to MRI scan.
- The (atrial, right or left ventricular) lead has not been replaced or repositioned within 6 weeks prior to MRI scan or between MRI scan and the one-month post-MRI visit.
- The VPCTs of RV at the pre-MRI must be $\leq 2.0V$. This is because subjects with a higher VPCT cannot have an MRI per CIP

To be a valid PCT measurement, the pulse width must be set to 0.4ms and a printed pacing capture threshold testing strip must be available to confirm the pulse width and capture threshold reported.

The pre-MRI period value will be the pre-MRI period PCT measurement. For the post-MRI period PCT value, the PCT value on the one-month post-MRI period CRF will be used. If that does not exist or is not valid, the PCT measured immediately post-MRI will be used instead.

Medtronic Business Restricted

[figure not shown]
China CIED 3.0T MRI Performance Study Clinical Investigation Plan

MDT23009

Version 2.0

Page 45 of 60

Medtronic

Medtronic Business Restricted

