Investigation Purpose	The purpose of this study is to confirm safety and effectiveness of the SureScan CIED System in the clinical MRI environment when subjects receive 3.0T MRI scans without positioning restrictions (MRI scans may occur anywhere on the body).
Product Status	Market released
Primary Objective(s) and/or Endpoint(s)	
To demonstrate the safety of SureScan system CIED in clinical 3.0T MRI environment within 1 month post-MRI scan.
 
Endpoint Definition
 
The occurrence of any of the following within 30 days after the 3.0T MRI visit will be considered an MRI-related event for IPG:
 
 ○ Medical advisor-assessed MRI-related complication within 30 days post-MRI ○ Medical advisor-assessed right ventricular MRI-related loss of capture within 30 days post-MRI 
The occurrence of any of the following within 30 days after the 3.0T MRI visit will be considered an MRI-related event for ICD/CRTD:
 
 ○ Medical advisor-assessed MRI-related complication within 30 days post-MRI ○ Sustained tachyarrhythmia originating during SureScan programming, requiring immediate treatment (defined as ATP, device shock, or external shock) as assessed by a medical advisor. ○ Medical advisor-assessed right ventricular MRI-related loss of capture within 30 days post-MRI
Secondary Objective(s) and/or Endpoint(s)	To characterize changes in atrial and ventricular pacing capture thresholds (APCT and VPCT) from pre-MRI to 1-month post-MRI scan

Medtronic Business Restricted

China CIED 3.0T MRI Performance Study Clinical Investigation Plan

MDT23009

Version 2.0

Page 11 of 60

Medtronic

	
Endpoint Definition
 
PCTs to be evaluated include:
 
○ Atrial pacing capture threshold (if applicable)○ Ventricular pacing capture threshold (both right and left ventricular lead if applicable)
--	---

Study Design	
The China CIED 3.0T MRI performance study is a prospective, multi-site, single-arm, interventional post-market study. Subjects who were implanted with an SureScan system CIED (including device and lead) over 6 weeks at the time of signing ICF will be enrolled. All subjects will have required follow-up visits at baseline, MRI scan and 1-month post-MRI. The MRI scan will occur in subjects implanted over 6 weeks.

Sample Size	64 patients

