5.1.2 Secondary Objective

To characterize changes in atrial and ventricular pacing capture thresholds (APCT and VPCT) from pre-MRI to one month post-MRI scan

Endpoint Definition

The effectiveness of the Surescan MRI CIED device will be measured by the following parameters

[figure not shown]
- Atrial pacing capture threshold (if applicable)
- Ventricular pacing capture threshold (both right and left ventricular lead if applicable)

These parameters will be measured pre-MRI scan, immediately post MRI scan and 1-month post MRI scan.

Rationale

Medtronic Business Restricted

While PCT and sensing amplitude changes will contribute to the effectiveness objective, the increased PCT will affect the pacing effectiveness and the lifetime of device.

6. Study Design

The China CIED 3.0T MRI Performance study is a prospective, non-blinded, multi-site, interventional post-market study. The study is expected to be conducted at mainland China. Participating devices are expected to include single/dual chamber transvenous IPG, single/dual chamber ICD and CRTD.

The number of enrolled subjects in the study is 64 considering the attrition. To ensure a reasonable distribution of experience and minimize site bias in study results, the maximum number of subjects enrolled at each site will be capped at 30% of total subjects enrolled. All subjects will have required follow-up visits at baseline, MRI visit, 1-month post-MRI. The MRI scans will occur at the MRI visit. The MRI scan region will be determined by investigator according to the subject's clinical condition.

Ethics Committee approval of the study CIP and informed consent must be obtained prior to the site enrolling patients. Subject medical history will be verified to ensure patients meet all the inclusion and none of the exclusion criteria.

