7.1.1 System/Product Component

MR Conditional IPGs

System configurations include a combination of a SureScan IPG, a pacing lead in the right atrium and ventricle (for dual chamber systems) or right ventricle only (single chamber IPG). All system components need to be Medtronic SureScan MR conditional products. Refer to Table 1 for details of current Medtronic MR conditional IPG system components approved for 1.5 and 3.0T MR conditional labeling in mainland China.

Table 1: Medtronic MR Conditional IPG Components

Component	Model Number
Pacing Leads	

Medtronic Business Restricted

Component	Model Number

MR Conditional ICDs

System configurations include a combination of a SureScan ICD, a pacing lead in the right atrium and ventricle (for dual chamber systems) or right ventricle only (single chamber ICD). All system components need to be Medtronic SureScan MR conditional products. Refer to Table 2 for details of current MR conditional ICD system components approved for 1.5 and 3.0T MR conditional labeling.

Table 2: Medtronic MR Conditional ICD Components

Component	Model Number
Pacing Leads	
Defibrillator Leads	

Medtronic Business Restricted

China CIED 3.0T MRI Performance Study Clinical Investigation Plan

MDT23009

Version 2.0

Page 18 of 60

Medtronic

Component	Model Number

MR Conditional CRTD

System configurations include a combination of a SureScan CRT-D devices, a pacing lead in the right atrium or 6725 pin plug, a defibrillator lead in the right ventricle, and a left ventricular lead. All system components need to be Medtronic SureScan MR conditional products. Refer to Table 3 for details of current MR conditional CRT-D system components approved for 1.5 and 3.0T MR conditional labeling.

Table 3: Medtronic MR Conditional CRTD Components

Component	Model Number
Pacing Leads	
Defibrillator Leads	
Left Heart Leads:	

Medtronic Business Restricted

8. Study Site Requirements

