7.9.2.2 Endpoint Definition

If applicable, PCTs to be evaluated include:

- APCT of atrial lead for subjects with an IPG device
- APCT of atrial lead and VPCT of right ventricular (RV) lead for subjects with an ICD device
- APCT of atrial lead and VPCTs of right ventricular (RV) and left ventricular (LV) leads for those with a CRT-D device.

PCTs of each subject will be measured prior to the 3.0T MRI scan and at the one-month post-MRI.

Change in PCT is defined as PCT measured at one-month post-MRI subtracts that measured prior to a 3.0T MRI scan. Proportion of subjects with an increase less than or equal to 0.5V in APCT or VPCTs from pre-MRI to one-month post-MRI will also be used to characterize the efficacy performance of SureScan with respect to PCTs.

If the 1-month post-MRI APCT or VPCT is missing, the PCT measured immediately post-MRI will be used instead.

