7.9.2.5 Analysis Methods

The change in PCT is the PCT measured at one-month post-MRI visit subtracts that measured prior to a 3.0T MRI scan. Descriptive statistics will be provided for changes in APCT and VPCTs, respectively.

In addition, the percentage of subjects with an increase less than or equal to 0.5V from pre- to one month post-MRI in APCT and VPCTs will be determined.

[figure not shown]

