7.9.2.6 Determination of Subjects/Data for Analysis

To be included in the analysis, all the following must be met:

- The subject must undergo a 3.0T MRI scan.
- The subject must have valid PCT measurements pre- and post-MRI (see paragraph below for definitions).
- The (atrial, right or left ventricular) lead is not dislodged within 6 weeks prior to MRI scan.
- The (atrial, right or left ventricular) lead has not been replaced or repositioned within 6 weeks prior to MRI scan or between MRI scan and the one-month post-MRI visit.
- The VPCTs of RV at the pre-MRI must be $\leq 2.0V$. This is because subjects with a higher VPCT cannot have an MRI per CIP

To be a valid PCT measurement, the pulse width must be set to 0.4ms and a printed pacing capture threshold testing strip must be available to confirm the pulse width and capture threshold reported.

The pre-MRI period value will be the pre-MRI period PCT measurement. For the post-MRI period PCT value, the PCT value on the one-month post-MRI period CRF will be used. If that does not exist or is not valid, the PCT measured immediately post-MRI will be used instead.

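### The device-by-device endpoint lists in CIP 14.3 and SAP 7.9.2.2 leave out the right ventricular threshold for pacemaker (IPG) subjects, against the plan's own definition of the secondary endpoint

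*Combined protocol and SAP*

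**What the plan says.** Three places define the secondary endpoint generally. The synopsis, CIP 5.1.2 and SAP 4.1.2 each list the atrial threshold where applicable and "Ventricular pacing capture threshold (both right and left ventricular lead if applicable"). None limits this by device. CIP 5.1.2 and SAP 4.1.2 add: "These parameters will be measured pre-MRI scan, immediately post MRI scan and 1-month post MRI scan".

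Two places then assign thresholds by device. The lists in CIP 14.3 and SAP 7.9.2.2 give ICD subjects the atrial and RV thresholds, and CRT-D subjects the atrial, RV and left ventricular (LV) thresholds. For pacemakers both say only "APCT of atrial lead for subjects with an IPG device". The SAP list opens with "If applicable, PCTs to be evaluated include"; the CIP list has no such qualifier.

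CIP 7.1.1 describes the pacemaker system as having "a pacing lead in the right atrium and ventricle (for dual chamber systems) or right ventricle only (single chamber IPG"). CIP section 6 expects both single- and dual-chamber pacemakers in the study.

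The rest of the analysis text makes no exception for pacemakers. SAP 7.9.2.5 says "Descriptive statistics will be provided for changes in APCT and VPCTs, respectively". The inclusion rules in SAP 7.9.2.6 are written by lead, for example "The (atrial, right or left ventricular) lead is not dislodged within 6 weeks prior to MRI scan".

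**The concern.** The general definition makes the RV threshold applicable to every pacemaker subject, because every pacemaker system has an RV lead. The lists name that threshold for the other two device types and omit it for this one. Neither document gives a reason.

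Two analysts working from the same plan could therefore report the only secondary endpoint on different sets of subjects. One would follow the objective and the analysis methods and include pacemaker RV pairs. The other would program from the list and leave them out. The SAP exists to settle such choices before the data are analysed, and here it leaves the choice open.

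The measures at stake are the paired RV change from pre-MRI to one month and the proportion with an RV rise of 0.5 V or less. Pacemaker RV values would still appear in the before-and-after summaries of SAP 7.7, but that section specifies neither measure.

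**Working it through.** **Step 1: set the passages side by side.**

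| Source | Pacemaker | ICD | CRT-D |
|---|---|---|---|
| Leads present (CIP 7.1.1) | RV always; atrial if dual chamber | RV always; atrial if dual chamber | RV and LV; atrial lead or pin plug |
| Synopsis, CIP 5.1.2, SAP 4.1.2 | Atrial if present, RV | Atrial if present, RV | Atrial if present, RV, LV |
| CIP 14.3 list | Atrial only | Atrial, RV | Atrial, RV, LV |
| SAP 7.9.2.2 list | Atrial only, if applicable | Atrial, RV, if applicable | Atrial, RV, LV, if applicable |

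The rows agree on ventricular thresholds for ICD and CRT-D. They disagree only in the pacemaker column.

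**Step 2: can the SAP's qualifier reconcile them?** No. It can remove a listed threshold when the lead is absent, but it cannot add one that is not listed. For a single-chamber pacemaker it removes the atrial threshold and leaves nothing.

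**Step 3: is there a sign of a deliberate exclusion?** None was found.
- The objective heading both lists covers atrial and ventricular thresholds.
- The analysis methods and the lead-based inclusion rules apply to all devices.
- The 0.5 V rationale in CIP 14.3 cites earlier studies, two of which CIP 14.2 identifies as pacemaker studies.
- SAP 7.11 declares no change from the CIP.
- The primary endpoint counts RV loss of capture in pacemaker subjects.

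**Step 4: size.** The documents do not give the device mix. Two assumptions are made: 30% to 70% of subjects have a pacemaker, and all 54 evaluable subjects (the minimum in CIP 14.5) have a valid RV pair. The second is an upper bound on completeness.

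- RV pairs affected: 0.30 × 54 = 16.2, about 16; 0.70 × 54 = 37.8, about 38.
- RV pairs remaining: 54 − 16 = 38; 54 − 38 = 16.
- Weight of one subject in the RV percentage: 100/54 = 1.85 points with everyone included; 100/38 = 2.63 and 100/16 = 6.25 points under the literal list.

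**Step 5: the primary objective.** With n = 54 and success declared at 53 or more event-free subjects, the exact one-sided alpha at 0.90 is 0.0237 and the power at 0.995 is 0.9699. Both match the PASS output in SAP section 6. Enrolment of 54/(1 − 0.15) = 63.5, rounded up to 64, also matches. None of these figures depends on how the secondary endpoint list is read.

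**Step 6: a smaller point in the same list.** Without the qualifier, CIP 14.3 lists an atrial threshold for single-chamber ICDs and for CRT-D systems built with "a pacing lead in the right atrium or 6725 pin plug" where the plug is used. Such subjects have no atrial lead.

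**The case against.** The best defence is that the plan can be read harmoniously. Both lists are introduced by the word *include*, which need not be exhaustive. The section title, objective, analysis methods and inclusion rules all refer to ventricular thresholds without restriction. An analyst programming from SAP 7.9.2.5 and 7.9.2.6 would include pacemaker RV pairs, so the bullet looks like a drafting omission. This shows that an inclusive reading is available and probably intended. It does not remove the other reading, because a list that goes device by device and names RV for two of three types invites the inference that the third is excluded.

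Other parts of the defence stand:
- The endpoint has no hypothesis and no performance requirement, so no conclusion turns on it.
- Thresholds are tested whatever the device (CIP 10.7 and 10.8), so no data are lost and either analysis can be run.
- The 30% to 70% range has no source in the documents, and 54 is the minimum for the primary objective, not the size of the threshold analysis set. The figures illustrate scale and are not evidence of bias.
- The missing qualifier in CIP 14.3 is cosmetic. The synopsis and CIP 5.1.2 already carry it for the atrial threshold, and a subject with no atrial lead cannot have a valid atrial measurement. No result would change.

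**Conclusion.** The concern holds and should be fixed. The device lists in CIP 14.3 and SAP 7.9.2.2 contradict the endpoint definition in the synopsis, CIP 5.1.2 and SAP 4.1.2. This conclusion rests on the text alone and needs no assumption.

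The consequence is confined to which subjects enter the descriptive RV summaries. On the assumed device mix, the literal list would remove 16 to 38 of at most 54 RV pairs, and one subject would move the RV percentage by 2.6 to 6.25 points instead of 1.9. The primary objective and the sample size of 54 evaluable and 64 enrolled are untouched.

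**What to change.** In CIP 14.3 and SAP 7.9.2.2, give the pacemaker bullet the same content as the ICD bullet: the atrial lead threshold and the RV lead threshold. As a tidy-up, open the CIP 14.3 list with the qualifier that SAP 7.9.2.2 already uses, so that systems without an atrial lead are covered in both documents.

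The text change is one bullet in each document and two words in the CIP. No new measurements are needed.

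The procedural cost depends on the route. A CIP revision needs ethics committee approval before it is implemented (CIP 15.1 and 16.6). CIP 14.1 requires an amendment for a changed analysis method only when a principal feature is altered; other changes are justified in the clinical study report. Because this correction restores the definition already in CIP 5.1.2, a SAP revision made before analysis and noted in the study report may be enough, with CIP 14.3 corrected at the next amendment.
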